#### 5.2.2.4.2 Cisplatin

Use the actual body weight for all patients. There should be no dose modifications because of obesity.

Cisplatin dose can be reduced up to 2 times if AEs occur (1st dose reduction of 25% to 30mg/m^2 and then subsequently to 23mg/m^2). However, if AEs as listed below continue to occur despite 2 subsequent dose reductions, therapy should be discontinued permanently. Chemotherapy dose should never be escalated.

Neutropenia: If on the day of scheduled treatment with Cisplatin the absolute neutrophil count (ANC) is < 1000/mm^3, hold chemotherapy treatment but not the radiation until ANC  $\geq$  1000/mm^3, then treat at 25% dose reduction. Neutropenic fever (i.e. any fever  $>$  38.5°C with an ANC <1000/mm^3) will require a 25% dose reduction of the next Cisplatin dose.

Thrombocytopenia: If on the day of scheduled treatment with Cisplatin the platelet count is < 75,000/mm^3, hold chemotherapy treatment but not the radiation until platelets are  $\geq$  75,000/mm^3, then treat at 75% dose.

Neurotoxicity: If grade 2 neurotoxicity develops, hold Cisplatin (but continue RT) until toxicity improves to < grade 1, then reduce the following Cisplatin dose by 25%. If any signs of grade 3 or greater neurotoxicity occur, discontinue Cisplatin, but continue RT.

Renal Adverse Events: Cisplatin dose should be based on the serum creatinine or creatinine clearance immediately prior to the second and third Cisplatin dose using the following guidelines:

Note: If creatinine is > 1.5 mg/dl, creatinine clearance must be calculated (Cockcroft-Gault) in order to make dose adjustment. If the calculated clearance is 50 mL/min or above, a 24-hour urine collection is not needed, but if the calculation is less than 50 mL/min, a 24-hour urine collection is mandated, and the Cisplatin dose will be determined as follows:

Serum Creatinine Creatinine Clearance Cisplatin Dose (Dose reductions should be made from current dose level)

$\leq$  1.5 mg/dl or > 50 ml/min then administer full dose

> 1.5 mg/dl and 40-50 ml/min then administer at 25% dose reduction

> 1.5 mg/dl and < 40 ml/min Hold drug\*

\*Cisplatin should be held (but the RT continued) and the creatinine measured weekly, until it is < 1.5 mg/dl or the creatinine clearance is > 50 ml/min, and then the next and following doses of Cisplatin should be given at a dose reduction of 25%.

Nausea and Vomiting: Maximum supportive therapy will be given, and Cisplatin will be continued at full dose for  $\leq$  grade 2 nausea and vomiting. For grade 3 nausea and vomiting refractory to supportive therapy, Cisplatin will be held until recovery to < grade 2. No dose reductions will be made.

Mucositis: Significant mucositis (grade 3-4, CTCAE, v. 4) is expected from radiation and Cisplatin and should not be a reason for a treatment break, unless it significantly interferes with fluid intake or nutrition. Aggressive supportive care is encouraged as well as consideration of a PEG tube if not already

done.

Ototoxicity: For clinical hearing loss not requiring a hearing aid, reduce Cisplatin by 2 dose levels (23mg/m^2). For hearing loss requiring a hearing aid, discontinue Cisplatin. For grade 2-3 tinnitus (CTCAE, v. 4) at the time of retreatment, hold Cisplatin until improvement to grade 1 or less and then reduce the following doses of Cisplatin by 2 dose levels. If tinnitus does not improve to grade 1 or less by the last day of radiation therapy, discontinue Cisplatin. An audiogram is recommended when there is any report of significant change in hearing and/or an increase in tinnitus.

Other Toxicities: For any other grade 3-4 adverse events, hold Cisplatin until toxicities have recovered to grade 1 or less. Dose may be reduced by 1 or 2 dose levels for next treatment if felt necessary by discretion of investigator.

If any doses of Cisplatin are skipped due to hematologic, neurologic, renal, or other adverse events, these doses will NOT be made up at end of treatment. Cisplatin will continue only during time of radiation treatment. If a weight change of  $\geq 10\%$  occurs, the following Cisplatin doses should be adjusted.

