#### Cisplatin

Cisplatin will be given at 40mg/m^2 starting concurrently with radiation one week after first post-surgery Pembrolizumab dose is given. Cisplatin will be given weekly for 6 doses during the radiation treatment. Any skipped doses will not be made up at the completion of radiation therapy.

**Formulation:** Each vial contains 10 mg of DDP, 19 mg of sodium chloride, 100 mg of mannitol, and hydrochloric acid for pH adjustment. One vial is reconstituted with 10 ml of sterile water. The pH range will be 3.5 to 4.5. Cisplatin injection also is available from the manufacturer in aqueous solution, each ml containing 1 mg Cisplatin and 9 mg NaCl and HCl or NaOH to adjust pH.

**Mechanism of Action:** The dominant mode of action of Cisplatin is inhibition of the incorporation of DNA precursors, although protein and RNA synthesis are also inhibited. Although Cisplatin is thought to act as an alkylating agent, there are data to indicate that its mode and sites of action are different from those of nitrogen mustard and other standard alkylating agents.

**Administration:** Cisplatin will be given as a bolus, infused over 1-2 hours along with appropriate hydration and anti-emetics.

**Storage and Stability:** Reconstituted solution of Cisplatin is stable for 20 hours when stored at 27°C and should be protected from light if not used within 6 hours. The vials and injection should not be refrigerated. Cisplatin has been shown to react with aluminum needles, producing a black precipitate within 30 minutes.

**Adverse Events:** Human toxicity includes nausea, vomiting, renal toxicity (with an elevation of BUN and creatinine and impairment of endogenous creatinine clearance, as well as renal tubular damage, which appears to be transient), ototoxicity (with hearing loss that initially is in the high-frequency range, as well as tinnitus), and hyperuricemia. Much more severe and prolonged toxicity has been observed in patients with abnormal or obstructed urinary excretory tracts. Myelosuppression, often with delayed erythrosuppression, is expected as well.

**Supply:** Cisplatin is commercially available. The use of drug(s) or combination of drugs in this protocol meet the criteria described under Title 21 CFR 312.2(b) for IND exemption.

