	Pre-screening (Visit 1)	Main Study Screening (Visit 2) P			1	2	3	4	5	6	7	8	9	10	NA	Safety Follow-up n	Survival Follow-Up a	
Treatment Dose Title:			Pre-Surgery Dose P															
Scheduling Window (Days):	-35 to -7	-22 to -7	-21 to -7	0	28 to 77	± 1	± 1	± 1	± 1	± 1	± 1	± 3	± 3	± 3	± 14	At time of Discon c	30 days and 3 months post discon	+/- 2 weeks
Adjuvant Treatment (Week):					1	2	3	4	5	6	7	10	13	16	19	(20 d )	20 d	
ECOG Performance Status		X	X		X			X				X	X	X	X	X		
Laboratory Procedures/Assessments: analysis performed by LOCAL laboratory																		
Pregnancy Test – Urine or Serum -HCG		X																
CBC with Differential m		X		X k	X	X	X	X	X	X	X	X	X	X	X	X		
Comprehensive Serum Chemistry Panel j, m		X		X k	X	X	X	X	X	X	X	X	X	X	X	X		
Urinalysis		X			X			X			X			X		X		
T3, FT4 and TSH		X		X k	X			X			X			X		X		
PT/INR, PTT		X		X k	X			X			X			X		X		
Efficacy Measurements																		
Tumor Imaging f		X													X			

Trial Period:	Screening Phase		Pre-surgery Dose	Surgery	Adjuvant Treatment										End of Treatment	Post-Treatment		
	Pre-screening (Visit 1)	Main Study Screening (Visit 2) P			1	2	3	4	5	6	7	8	9	10	NA	Safety Follow-up n	Survival Follow-Up a	
Treatment Dose Title:			Pre-Surgery Dose P													Discon		
Scheduling Window (Days):	-35 to -7	-22 to -7	-21 to -7	0	28 to 77	± 1	± 1	± 1	± 1	± 1	± 1	± 3	± 3	± 3	± 14	At time of Discon c	30 days and 3 months post discon	+/- 2 weeks
Adjuvant Treatment (Week):					1	2	3	4	5	6	7	10	13	16	19	(20 d )	20 d	
Tumor Biopsies/Archival Tissue Collection/Correlative Studies Blood																		
Archival or Newly Obtained Tissue Collection g		X		X														
Correlative Studies Blood Collection g		X		X k	X		X											

Trial Period:	Screening Phase		Pre-surgery Dose	Surgery	Adjuvant Treatment										End of Treatment	Post-Treatment		
Treatment Dose Title:	Pre-screening (Visit 1)	Main Study Screening (Visit 2) P	Pre-Surgery Dose P		1	2	3	4	5	6	7	8	9	10	NA	Discon	Safety Follow-up n	Survival Follow-Up a

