Adjuvant Treatment (Week):					1	2	3	4	5	6	7	10	13	16	19	(20 d )	20 d	
i. See Table 5 for full list. j. Pembrolizumab to be given 30 minutes before Cisplatin on days administered together. k. To be drawn before surgery (day of surgery or up to 4 days prior acceptable). l. This assessment must be performed prior to the start of radiation treatment. m. For the Radiation and Pembrolizumab arm (intermediate risk), safety labs are not required on non-pembro administration weeks. n. 3 month post-discontinuation visit is highly recommended, but optional. o. Informed consent may be obtained on the same day as screening procedures or on the same day as the pre-surgical pembro dose provided the subject has been given a copy of the consent form in advance of this visit to review or adequate time for review on the same-day has been documented. p. Pre-surgical dose and pre-screening visits may occur on the same day as long as consent is obtained, and eligibility is confirmed prior to pembro dose. All screening labs should be performed within 10 days of treatment initiation (the pre-surgical dose of Pembrolizumab).																		

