### 7.1.3.2 Pharmacodynamic Evaluations

#### 7.1.3.2.1 Peripheral Blood Monocyte Cell (PBMC) Isolation

40 mls of whole blood will be collected in purple top EDTA tubes at 4 timepoints prior to Pembrolizumab administration (on day -28-6 before resection), on day of resection (day 0), prior to Pembrolizumab administration on adjuvant week 1, before 2nd chemotherapy (Cisplatin) and radiation on week 3 (see study calendar) and transferred at room temperature within 24 hours to UCCC.

PBMCs and plasma will be separated by Ficoll centrifugation at UCCC. Plasma will be frozen and stored at -80°C. PBMCs will be either cryopreserved or immediately processed for flow cytometry and functional analysis. Stored plasma will be used for cytokine assays. Please see procedure manual for full details.

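### The cisplatin renal dosing rule is tied to doses 2 and 3, and nothing expressly extends it to doses 4 to 6 of the six weekly doses

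*Combined protocol and SAP*

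**What the plan says.** The regimen is stated in Section 5.2.3 under Cisplatin: "Cisplatin will be given weekly for 6 doses during the radiation treatment". Table 2 and Sections 4.2.2.2 and 5.2.2.2.1 agree on six doses, and the first two give 40 mg/m² per dose.

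The renal rule is in Section 5.2.2.4.2. It sets the dose from serum creatinine or creatinine clearance "immediately prior to the second and third Cisplatin dose", and a note and a three-row table follow:

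- Creatinine at or below 1.5 mg/dl, or clearance above 50 ml/min: full dose.
- Creatinine above 1.5 mg/dl with clearance 40–50 ml/min: 25% reduction from the current level.
- Creatinine above 1.5 mg/dl with clearance below 40 ml/min: hold, recheck weekly, then give the next and later doses at a 25% reduction.

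The same section has a general stopping rule: "However, if AEs as listed below continue to occur despite 2 subsequent dose reductions, therapy should be discontinued permanently". Its catch-all for unlisted events reads: "For any other grade 3-4 adverse events, hold Cisplatin until toxicities have recovered to grade 1 or less".

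On monitoring, the flow chart in Section 6.1 marks the "Comprehensive Serum Chemistry Panel" at every adjuvant week from 1 to 7, and Table 5 includes creatinine in that panel. Note m relaxes this for the intermediate-risk arm alone, where "safety labs are not required on non-pembro administration weeks". Section 7.1.3.1 requires laboratory results to be reviewed and judged acceptable before each dose of trial treatment.

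**The concern.** The renal rule names two doses of a six-dose course, and no reason is given for stopping at dose 3. The protocol itself lists renal toxicity among cisplatin's adverse events (Section 5.2.3) and cites renal dysfunction as a problem with the bolus regimen (Section 4.2.2.2). Stopping at dose 3 therefore looks like a drafting error and not a choice. The wording would suit a three-dose bolus schedule such as the one described in Section 4.2.2.2, but that origin is an inference and the point does not depend on it.

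What is at stake is consistent and safe dosing. Section 8.1.4 names six sites besides the lead centre. Faced with the same creatinine result in the second half of the course, one site could apply the table and another could decide case by case.

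**Working it through.** The plan states no figure to reproduce. The check is a reading of the text and a count of doses.

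**1. Which weeks are affected.** Adjuvant weeks are numbered from the first post-surgery pembrolizumab infusion (Section 6.1, note a), and cisplatin starts one week later (Section 5.2.3), so dose 1 is in week 2. Section 7.1.3.2.1 agrees, placing a blood draw "before 2nd chemotherapy (Cisplatin) and radiation on week 3". On a weekly schedule dose 3 is in week 4, and doses 4, 5 and 6 are in weeks 5, 6 and 7.

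**2. How much of the course is affected.**

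- Planned total: 6 × 40 = 240 mg/m².
- Doses 2–3, expressly covered: 2 × 40 = 80 mg/m² (80/240 = 33%).
- Doses 4–6, not expressly covered: 3 × 40 = 120 mg/m² (120/240 = 50%).
- Dose 1 precedes any cisplatin exposure.

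**3. Does the limit fit the rest of Section 5.2.2.4.2?** It does not.

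- The thrombocytopenia rule opens "If on the day of scheduled treatment with Cisplatin the platelet count is", and the neutropenia rule has the same form. Both apply at any dose.
- The neurotoxicity and ototoxicity rules carry no dose number.
- The stopping rule requires listed events to persist after two reductions. If those were renal reductions at doses 2 and 3, persistence can be judged only at dose 4 or later. The section therefore presupposes renal assessment beyond dose 3.

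**4. Does another provision supply the rule for doses 4–6?**

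| Provision | What it gives | What it lacks |
|---|---|---|
| Weekly chemistry (6.1, Table 5) | A creatinine value | Any cisplatin action |
| Pre-dose laboratory review (7.1.3.1) | A general check | Renal threshold, reduction or hold |
| Other Toxicities (5.2.2.4.2) | A hold for other grade 3–4 events | Cover for moderate rises; arguably any renal event, since these have their own heading |
| Carry-forward of the 25% reduction (5.2.2.4.2) | Reaches later doses | Works only after a hold made under the table |
| Nephritis row (Table 3) | Action on pembrolizumab | Any cisplatin action |

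**5. What the two readings mean for one patient.** Assume full doses until the first abnormal result, with creatinine above 1.5 mg/dl. The reduced level is 40 × 0.75 = 30 mg/m². It carries forward because Section 5.2.2.4.2 bars escalation, and skipped doses are not made up.

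- Clearance 40–50 ml/min before dose 4, table applied once: 3 × 40 + 3 × 30 = 210 mg/m².
- Clearance below 40 ml/min before dose 4, recovered by dose 5: 3 × 40 + 0 + 2 × 30 = 180 mg/m².
- Table read as ending at dose 3: up to 240 mg/m² in either case.

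The differences are up to 30 and 60 mg/m². They shrink if the rise comes later: at dose 6, a single reduction gives 5 × 40 + 30 = 230 mg/m² and a hold gives 5 × 40 = 200 mg/m².

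**The case against.** The best reply is that the section never excludes doses 4–6. The note under the rule is triggered by a creatinine value and not by a dose number: above 1.5 mg/dl, clearance must be calculated, and below 50 ml/min a 24-hour urine collection is required and the table sets the dose. A sensible site would follow it at any dose. The general reduction rule has no dose limit either, the carry-forward after a hold reaches later doses, and the text on skipped doses mentions renal events without a dose number. Section 7.1.1.7 also says standard therapies are prepared and administered according to the product label. Finally, the 240 mg/m² figure in the hold example requires an investigator to accept a clearance below 40 ml/min and still give full-dose cisplatin, which nothing in the protocol directs.

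Part of this stands. The text does not forbid using the table later, renal function is monitored, many clinicians would adjust the dose anyway, and 240 mg/m² is an upper limit. But the note and table sit beneath the sentence that names doses 2 and 3 and are introduced as its guidelines, so a literal reader can take them as limited to those doses. The label clause states no renal threshold. That the section seems to expect renal action at dose 4 or later shows that the wording does not match the intent; it does not supply the missing instruction.

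It is also fair to note that dose 1 lies outside the table and rests on the pre-dose laboratory review. The rule is written for toxicity after cisplatin exposure, so starting at dose 2 is coherent in a way that stopping at dose 3 is not.

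**Conclusion.** The concern holds as stated. The numeric renal rule is tied to doses 2 and 3 and is not expressly extended to doses 4–6, which make up half the planned exposure (120 of 240 mg/m²). A new moderate creatinine rise in adjuvant weeks 5–7 is left to judgement. For a rise first seen before dose 4, the two readings differ by up to 30 mg/m² when a single reduction applies, or up to 60 mg/m² when one dose is held.

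These amounts are illustrations for one patient and assume full doses up to the first abnormal result. The documents give no renal event rate, so the number of patients affected cannot be stated. The point does not say that renal monitoring is absent, and it makes no claim about disease-free survival or the dose-limiting toxicity count. It is a safety rule whose scope does not match the regimen and should be corrected.

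**What to change.** In Section 5.2.2.4.2, under Renal Adverse Events, replace the reference to the second and third doses with wording that applies the rule *immediately before each cisplatin dose after the first*. Leave the thresholds, the 25% reduction and the hold rule as they are.

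The cost is one phrase. Creatinine is already drawn every treatment week in the cisplatin arm, so the only possible extra test is the 24-hour urine collection that the rule already requires when calculated clearance is below 50 ml/min. The design and the statistical analysis do not change.

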### 5.2.3 Timing of Dose Administration

Trial treatment should be administered on Day 1 of each cycle after all procedures/assessments have been completed as detailed on the Trial Flow Chart (Section 6.0). Study Drug may be administered up to 3 days before or after the scheduled Day 1 of each cycle due to administrative reasons. Cisplatin should not be delayed more than 1 day of scheduled dose. Pembrolizumab should be given 30 minutes prior to Cisplatin dose on days in which they are administered together.

All trial treatments will be administered on an outpatient basis.

#### Cisplatin

Cisplatin will be given at 40mg/m^2 starting concurrently with radiation one week after first post-surgery Pembrolizumab dose is given. Cisplatin will be given weekly for 6 doses during the radiation treatment. Any skipped doses will not be made up at the completion of radiation therapy.

**Formulation:** Each vial contains 10 mg of DDP, 19 mg of sodium chloride, 100 mg of mannitol, and hydrochloric acid for pH adjustment. One vial is reconstituted with 10 ml of sterile water. The pH range will be 3.5 to 4.5. Cisplatin injection also is available from the manufacturer in aqueous solution, each ml containing 1 mg Cisplatin and 9 mg NaCl and HCl or NaOH to adjust pH.

**Mechanism of Action:** The dominant mode of action of Cisplatin is inhibition of the incorporation of DNA precursors, although protein and RNA synthesis are also inhibited. Although Cisplatin is thought to act as an alkylating agent, there are data to indicate that its mode and sites of action are different from those of nitrogen mustard and other standard alkylating agents.

**Administration:** Cisplatin will be given as a bolus, infused over 1-2 hours along with appropriate hydration and anti-emetics.

**Storage and Stability:** Reconstituted solution of Cisplatin is stable for 20 hours when stored at 27°C and should be protected from light if not used within 6 hours. The vials and injection should not be refrigerated. Cisplatin has been shown to react with aluminum needles, producing a black precipitate within 30 minutes.

**Adverse Events:** Human toxicity includes nausea, vomiting, renal toxicity (with an elevation of BUN and creatinine and impairment of endogenous creatinine clearance, as well as renal tubular damage, which appears to be transient), ototoxicity (with hearing loss that initially is in the high-frequency range, as well as tinnitus), and hyperuricemia. Much more severe and prolonged toxicity has been observed in patients with abnormal or obstructed urinary excretory tracts. Myelosuppression, often with delayed erythrosuppression, is expected as well.

**Supply:** Cisplatin is commercially available. The use of drug(s) or combination of drugs in this protocol meet the criteria described under Title 21 CFR 312.2(b) for IND exemption.

#### **5.2.4 Surgery**

Patients must have undergone gross total surgical resection no earlier than 7 days and no later than 21 days after initial Pembrolizumab administration.

##### **5.2.4.1 Surgical Quality Assurance Reviews**

The Surgical Oncology Co-Chair, [name], will perform a Quality Assurance Review after complete data for the first 20 cases enrolled has been received at UCCC. He will review pathology and operative reports for compliance with eligibility based on documentation of the pathologic descriptors for high-risk disease: extracapsular nodal extension or invasive cancer seen on microscopic evaluation of resection margins. [name] will perform the next review after complete data for the next 20 cases enrolled has been received at UCCC. The final cases will be reviewed within 3 months after this study has reached the target accrual or as soon as complete data for all cases enrolled has been received at UCCC, whichever occurs first.

#### **5.3 Stratification**

After surgical resection, patients will be stratified into two groups: high risk patients with proven positive surgical margins or extracapsular extension of lymph nodes or intermediate risk including all patients not meeting criteria for high risk. There is a small chance that although patients are identified clinically to require radiation prior to surgery, that the pathology will deem the patient to be low risk and radiation would not be considered standard of care. In the event, the investigator feels it is not in the best interest of patient to administer radiation (or radiation would not be considered standard of care), then patient may be withdrawn from the study.

#### **5.4 Concomitant Medications/Vaccinations (allowed & prohibited)**

Medications or vaccinations specifically prohibited in the exclusion criteria are not allowed while on treatment or in end of treatment follow-up period. If there is a clinical indication for one of these or other medications or vaccinations specifically prohibited during the trial, discontinuation from trial therapy or vaccination may be required. The investigator should discuss any questions regarding this with the Sponsor. The final decision on any supportive therapy or vaccination rests with the investigator and/or the subject's primary physician and decision must be discussed with PI to determine if patient remains eligible to receive treatment.

